4.3. FINAL ANALYSIS

All final, planned analyses identified in this SAP will be performed by IQVIA Biostatistics following final analysis database lock (all subjects have completed the study, outstanding data queries have been resolved and the database has been cleaned and finalized.). The PK/PD analysis will be conducted by the PK group, a separate analysis plan will be provided by PK group.

5. ANALYSIS POPULATION

5.1. STAGE 1 POPULATION

Screened Set (Screened) in stage 1

The screened set will contain all subjects who signed informed consent for stage 1.

Document: Statistical Analysis Plan

Author: [name]

Version Number: 1.1

Version Date: 18Jan2023

Template No.: CS_TP_BS016 Revision 5

Reference: CS_WI_BS005

Effective Date: 01Apr2018

All Randomized Set (Randomized) in stage 1

The randomized set will contain all subjects who are randomized into stage 1, no matter treated or not.

Full Analysis Set (FAS) in stage 1

The full analysis population (FAS) will contain all randomized subjects who receive at least one dose of study medication or placebo in stage 1. FAS will be based on the planned drug taken.

Modified Full Analysis Set (mFAS) in stage 1

The modified full analysis population (mFAS) will contain all randomized subjects who receive at least one dose of study medication or placebo in stage 1 except subjects without week 12 adapted mayo score due to COVID-19. mFAS will be based on the planned drug taken.

Per Protocol Set (PPS) in stage 1

The per-protocol set (PPS) will contain a subset of FAS subjects who do not have major protocol deviation in stage 1.

Definition of major protocol deviation in stage 1:

1. Any Major clinical protocol deviation of Randomization Criteria
2. Any Major clinical protocol deviation of Eligibility and Entry Criteria
3. Any prohibited concomitant medication in clinical protocol deviation
4. IP compliance below 80% or over 120%
5. Have no baseline Adapted Mayo score
6. Have no Week12 Adapted Mayo score
7. Week 12 Adapted Mayo Score is out of visit window
8. Any unblinding during stage 1
9. Any other critical clinical protocol deviations in stage 1

Definition of minor protocol deviation in stage 1:

Clinical protocol deviation except major protocol deviation happened in stage 1.

Document: Statistical Analysis Plan

Author: [name]

Version Number: 1.1

Version Date: 18Jan2023

Template No.: CS_TP_BS016 Revision 5

Reference: CS_WI_BS005

Effective Date: 01Apr2018

Safety Set (SS) in stage 1

The safety set (SS) will contain all randomized subjects who receive at least one dose of study medication or placebo. SS will be based on the actual drug taken.

5.2. STAGE 2 POPULATION

All Subjects Screened (Screened) in stage 2

The all subjects screened will contain all subjects who signed informed consent for stage 2.

Full Analysis Set (FAS) in stage 2

The full analysis set (FAS) will contain all screened subjects who receive at least one dose of study medication or placebo in stage 2. FAS will be based on the planned drug taken.

Per-Protocol Analysis Set (PPS) in Stage 2

The per-protocol set (PPS) will contain a subset of FAS subjects who do not have major protocol deviation in stage 2.

Definition of major protocol deviation in stage 2 sub-study 1:

1. Any Major clinical protocol deviation of Randomization Criteria
2. Any Major clinical protocol deviation of Eligibility and Entry Criteria
3. Any prohibited concomitant medication in clinical protocol deviation
4. IP compliance below 80% or over 120%
5. Have no baseline Adapted Mayo score
6. Have no Week48 Adapted Mayo score
7. Week48 Adapted Mayo Score is out of visit window
8. Any unblinding during stage 2
9. Any other critical clinical protocol deviations in stage 2

Document: Statistical Analysis Plan

Author: [name]

Version Number: 1.1

Version Date: 18Jan2023

Template No.: CS_TP_BS016 Revision 5

Reference: CS_WI_BS005

Effective Date: 01Apr2018

Definition of minor protocol deviation in stage 2:

Clinical protocol deviation except major protocol deviation happened in stage 2.

Safety Set (SS) in stage 2

The safety set (SS) will contain all randomized subjects who receive at least one dose of study medication or placebo in stage 2. SS will be based on the actual drug taken.

5.3. ALL STAGES (0.2MG ONLY) POPULATION

All Subjects Screened (Screened)

The Screened Set includes all subjects who signed informed consent for stage 1 and stage 2 in 0.2mg treatment group.

Full Analysis Set (FAS)

The full analysis set includes all randomized subjects who receive at least one dose of 0.2 mg study medication in stage 1 and stage 2, either sub-study 1 or sub-study 2.

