 - *Hepatitis B surface antigen (HBsAg), hepatitis B surface antibody (HBsAb) and hepatitis B core antibody (HBcAb) must be evaluated for all the patients at screening. Patients with positive hepatitis B surface antigen (HBsAg) will be excluded. HBV-DNA test should be carried out at screening if the subject is negative for Hepatitis B surface antigen, negative or positive for hepatitis B surface antibody, and positive for hepatitis B core antibody. The subject should be excluded from the study if HBV-DNA test result is positive, or he/her can be enrolled in the study in case of negative result of HBV-DNA test.
 - **An HCV viral load test should be carried out if HCV antibody (HCVAb) is positive. The subject should be excluded from the study in case of positive HCV viral load test result. If the HCV viral load test result is negative, the subject can be enrolled in the study.
- 39. The subject has any identified congenital or acquired immunodeficiency (e.g., common variable immunodeficiency, human immunodeficiency virus [HIV] infection, organ transplantation).
- 40. The subject has received any live vaccine within 30 days prior to screening, or subjects are scheduled for immunization with any live vaccine during the study or within 1 month after the last dose of the investigational product.
- 41. Positive syphilis antibody at screening.

42. Subjects with a history of more than one episode of herpes zoster, or a history of disseminated herpes zoster or disseminated herpes simplex.

Inclusion and exclusion criteria for subjects' entry into the study stage 2 from the stage 1: Inclusion criteria:

Subjects cannot enter the study stage 2 if any of the following criteria is not satisfied:

- 1. Subjects must be those with UC who participate in the study of CBP-307CN002 and have completed 12 weeks of treatment with CBP-307 or placebo in the stage 1 and have completed all the assessments (including colonoscopy) at study visit of week 12 in study stage 1.
- 2. Subjects have good compliance in stage 1, can understand all information about the study stage 2, and are able and willing to comply with the requirements specified in the study protocol.
- 3. Subjects or their legal representatives voluntarily sign informed consent forms for study stage 2.

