3. Exploratory clinical remission rate by adapted mayo score is added for clinical discussion as exploratory efficacy endpoint. Exploratory clinical remission rate by adapted mayo score is defined as a rectal bleeding subscore ≤ 1 and a stool frequency subscore ≤ 1 , with an Endoscopy subscore ≤ 1 [excluding friability].
4. 0.2 mg (all stages) analysis is added for a new population to analyse those patients who received 0.2 mg from initial - administration until end of treatment in the study.

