6. GENERAL CONSIDERATIONS

Analysis results will be presented using descriptive statistics. For categorical variables, the number and percentage of subjects in each category will be presented; for continuous variables, the number of subjects [n], mean, standard deviation [SD] or standard error [SE], median, minimum, and maximum will be presented. Statistical comparisons will be tested at two-sided alpha of 0.05 significance level, unless otherwise specified. Data collected in the study will be presented in by-subject listings for all subjects in the full analysis set (efficacy analysis) and safety analysis set

Document: Statistical Analysis Plan

Author: [name]

Version Number: 1.1

Version Date: 18Jan2023

Template No.: CS_TP_BS016 Revision 5

Reference: CS_WI_BS005

Effective Date: 01Apr2018

(safety analysis), unless otherwise specified. All by subject listings will be presented by treatment group, subject identification number in ascending order, unless otherwise specified.

For stage 1 analysis, the analysis period for subjects who enroll stage 2 will be from screening (baseline visit) in stage 1 until before the first dose of stage 2. And for subjects who will not enroll stage 2 (including screen failed subjects before randomization, randomized subjects but not treated, and subjects early discontinued in stage 1), the analysis period will be from screening (baseline visit) in stage 1 until end of study in stage 1. For stage 2 sub-study 1 analysis, the full/safety analysis population will be the randomized subjects who receive at least one dose of study medication or placebo in stage 2, but the analysis period will be from screening (baseline visit) in stage 1 until the end of study in stage 2. But for subjects who will enroll stage 2 sub-study 2, the analysis period will be the date of first dose of the open-label CBP307 0.2mg in stage 2 until the end of study in stage 2 since treatment is changed to open-label CBP307 0.2 mg QD.

For 0.2mg (all stages) group, the analysis period will be the date of first dose of initial administration until the end of stage 2 study, including stage 2 sub-study 1 and stage 2 sub-stage 2.

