Primary reasons for study discontinuation, as entered on the eCRF, will be tabulated; the reasons include subject didn't meet eligibility criteria(s), adverse event, significant protocol deviation, death, non-compliance problems, lost to follow-up, withdrawal by subject, study terminated by sponsor, pregnancy, lack of efficacy or disease progression, or other. COVID-19 will be presented separately after selected from other reasons in 'Other, Specify' category.

0.2mg only for all stages will present both stage 1 and stage 2 disposition.

Completed or discontinued from study, duration of study, and the reason for study withdrawal will be listed for each safety subject in the listings.

Major protocol deviation leading to subject being excluded from FAS in PPS and summary of all analysis sets will be presented for the safety set and be listed in the listings. Listing of

Document: Statistical Analysis Plan

Author: [name]

Version Number: 1.1

Version Date: 18Jan2023

Template No.: CS_TP_BS016 Revision 5

Reference: CS_WI_BS005

Effective Date: 01Apr2018

inclusion/exclusion criteria responses by subject will also be provided.

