14.3.2. MISSING DATA METHODS FOR SECONDARY EFFICACY

VARIABLES

For the quantitative efficacy endpoint (changes in the Mayo score at week 12), the MI, LOCF, and complete case analysis will be presented if the Mayo score is missing in FAS and mFAS population.

For the qualitative efficacy analyses, subjects with any missing individual rating at week 12 will be considered as non-responders.

Endoscopy video will be obtained during each endoscopy and will be sent to Bioclinica for

Document: Statistical Analysis Plan

Author: [name]

Version Number: 1.1

Version Date: 18Jan2023

Template No.: CS_TP_BS016 Revision 5

Reference: CS_WI_BS005

Effective Date: 01Apr2018

central reading and determination of the Mayo endoscopy score. The result of the central reading of the endoscopy will be used to ensure subject eligibility prior to randomization and to calculate the Mayo score at analysis time points specified in the SAP. The Mayo score used for clinical endpoints in the study will utilize the Mayo endoscopy score derived from the central reader. The Mayo endoscopic score read by the investigator will be used as the Mayo score for clinical endpoints in case central reading endoscope data is missing.

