- Percentage of subjects who achieve mucosal healing under endoscope at week 48 (at week 36 after treatment in sub-study 2)
- Change in the complete Mayo score at week 48 (at week 36 of treatment in sub-study 2) from week 12:
- Change in the adapted Mayo score at week 48 (at week 36 after treatment in sub-study 2) from week 12
- Percentage of Subjects Who Take Oral Corticosteroids at Baseline, Has Discontinued Treatment with Corticosteroids at Week 48 and Achieved Clinical Remission

Efficacy endpoint in all stages for 0.2mg only:

- Change in the adapted Mayo score from baseline
- Change in the complete Mayo score from baseline
- Percentage of subjects who achieve clinical response at week 12 and week 48
- Percentage of subjects who achieve clinical remission at week 12 and week 48
- Percentage of subjects who achieve mucosal healing under endoscope at week 12 and week 48

Change from Baseline by Visit in IBDQ Total and Subscale Scores by VisitSummary of Percentage of Subjects Who Take Oral Corticosteroids at Baseline, Has Discontinued Treatment with Corticosteroids at Week 48 and Achieved Clinical Remission

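### As written, the all-stages 0.2 mg analysis set holds only stage 2 entrants, so its week-12 and week-48 rates are conditional on entering stage 2

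*SAP*

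**What the plan says.** SAP section 5.3 defines the all-stages (0.2 mg only) full analysis set as randomised subjects who "receive at least one dose of 0.2 mg study medication in stage 1 and stage 2, either sub-study 1 or sub-study 2". The matching screened set is worded the same way: "all subjects who signed informed consent for stage 1 and stage 2 in 0.2mg treatment group". Section 6 adds that for this group "the analysis period will be the date of first dose of initial administration until the end of stage 2 study".

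Section 3.3, item 4, gives the purpose more loosely. The set is there to analyse "those patients who received 0.2 mg from initial - administration until end of treatment in the study", and entry to stage 2 is not mentioned.

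Two uses matter here:

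- Section 14.4.1 lists, for this group, "Percentage of subjects who achieve clinical response at week 12 and week 48", with the same pair of time points for remission and mucosal healing.
- Section 8 says that "0.2mg only for all stages will present both stage 1 and stage 2 disposition".

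The protocol (synopsis and section 5.4.2) makes stage 2 optional and admits only subjects who "have completed 12 weeks of treatment with CBP-307 or placebo in the stage 1 and have completed all the assessments (including colonoscopy") at week 12. SAP section 14.4.2 restricts the 0.2 mg only analysis to single-arm descriptive statistics.

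**The concern.** A set that needs a stage 2 dose is selected on what happened in stage 1. Subjects who stopped before week 12 or missed the week-12 colonoscopy cannot be in it. Neither can completers who declined stage 2 or failed its entry criteria. Protocol section 5.4.2 bars subjects who received a biologic, an immunosuppressant or higher-dose steroids after the first dose, and those whose drug-related adverse events made them unsuitable in the investigator's view. Section 5.4.4 allows withdrawal in stage 1 for lack of benefit. Much of this selection removes subjects in whom treatment failed or was not tolerated.

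The missing-data rule does not repair this. SAP section 14.3.2 says that "subjects with any missing individual rating at week 12 will be considered as non-responders", but such a rule acts only on subjects who are in the denominator.

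At stake is how the descriptive treat-through results for 0.2 mg are read. The report would give two week-12 rates for the same arm, both labelled full analysis set, on different denominators. A single-arm week-48 rate has no comparator that would reveal the selection.

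**Working it through.** **Step 1: who can be in the set.** Section 5.3 asks for dosing in stage 1 and in stage 2. A stage 2 dose requires stage 2 entry, and entry requires 12 weeks of treatment and all week-12 assessments. If the entry criteria are followed, every member is a stage 1 completer. Two stage 1 categories in SAP section 8, early discontinuation and completion without entering stage 2, must then be empty for this set. Item 4 of section 3.3 would accommodate a subject who took 0.2 mg and stopped in week 6; section 5.3 would not. The definition is narrower than its purpose.

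**Step 2: the denominator.** The documents give no size for this set, so the planned arm size serves as the starting point. The inputs are in SAP section 7.4: difference 1.2, SD 2.0, two-sided alpha 0.05, power 80%, dropout 15%.

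- n = 2 × SD² × (1.960 + 0.842)² / difference² = 2 × 4 × 7.85 / 1.44 = 43.6, rounded up to 44.
- 44 / 0.85 = 51.8, rounded up to 52. The planned figure of 52 per group reproduces. A t-based n of 45 gives 53.

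**Step 3: size of the effect under stated assumptions.** Let r be the number of responders and m the number who enter stage 2. If no non-entrant responded, the rate among all started is r/52, the rate in the set is r/m, and the ratio is 52/m.

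- 15% non-entry: 52 × 0.85 = 44.2, so m = 44 and the ratio is 52/44 = 1.18.
- 20% non-entry: 52 × 0.80 = 41.6, so m = 42 and the ratio is 52/42 = 1.24.

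| Responders (assumed) | Of 52 | Of 44 | Of 42 |
|---|---|---|---|
| 10 | 19.2% | 22.7% | 23.8% |
| 20 | 38.5% | 45.5% | 47.6% |
| 26 | 50.0% | 59.1% | 61.9% |

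The responder counts are assumptions; the documents give none. The 15% is the sample-size dropout allowance, and the 20% is the missing week-12 scores anticipated in SAP section 3.3. Neither is a forecast of stage 2 non-entry.

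**Step 4: can the direction reverse?** Take 20 responders of 52, 8 dropouts with no response, and 6 completers who do not enter stage 2. The set has 52 − 8 − 6 = 38 members. If q of the 6 responded, its rate is (20 − q)/38:

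- q = 0: 20/38 = 52.6%
- q = 3: 17/38 = 44.7%
- q = 5: 15/38 = 39.5%
- q = 6: 14/38 = 36.8%, below the 38.5% among all 52

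In this example the set's rate is the lower one only if all six were responders.

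**Step 5: week 48.** The same ratios apply if missing counts as non-response and no non-entrant is counted as a responder. However, the SAP rule names week 12, and protocol section 9.12 covers secondary categorical endpoints. Neither states a week-48 rule for this exploratory set. The gap matters because sub-study 1 subjects with recurrence and sub-study 2 subjects without response at week 24 are withdrawn, so missing week-48 ratings are built into the design.

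**The case against.** The strongest objection is that the wording may mean pooled across the stages. The heading says all stages, section 3.3 speaks of treatment from first dose to end of treatment, and planning stage 1 disposition for the set makes little sense if two of its categories must be empty. This shows that the intent is unclear, but it does not rescue the text. The screened-set wording and the analysis period both point to dosing in both stages. Read as dosing in either stage, the definition would admit placebo non-responders given open-label 0.2 mg in sub-study 2, contrary to section 3.3. The sentence needs correcting on either reading.

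The second objection concerns direction. A reader might infer that the rates are certainly inflated. The documents do not support that: completers may decline an optional stage, or be excluded on laboratory, ECG or lung-function findings, and such subjects may be responders. Dropouts may also have an early-termination Mayo score. This objection stands, so the excess is an expectation only.

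The third is that the unconditional results appear elsewhere. Week-12 rates are analysed on the stage 1 FAS, mFAS and PPS with missing as non-response, and disposition of all randomised subjects is tabulated by arm. This also stands and limits the consequence. It does not supply an unconditional week-48 rate for subjects started on 0.2 mg.

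Finally, a rate among those who continued is a legitimate descriptive quantity if labelled. That is accepted in the fix.

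**Conclusion.** The point holds in limited form. As written, the all-stages 0.2 mg full analysis set contains only stage 1 completers who entered stage 2. Its response, remission and healing rates are conditional on that entry, and its stage 1 discontinuation is zero by construction. The rates are expected, though not certain, to exceed those among all subjects started on 0.2 mg. With 52 dosed and no responder among non-entrants, the factor is 1.18 at 15% non-entry and 1.24 at 20%. Both non-entry rates, the responder counts and the zero response among non-entrants are assumptions. The excess shrinks as more non-entrants are responders.

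A reader might also infer that the estimate of 0.2 mg against placebo is biased. It is not affected: the primary and secondary stage 1 analyses use stage 1 sets that carry no stage 2 condition. The all-stages analysis is exploratory, single-arm and descriptive. It should be corrected because the change is small and the set is narrower than its own stated purpose.

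**What to change.** In SAP section 5.3, define the full analysis set along these lines: *all subjects randomised to 0.2 mg who receive at least one dose of study medication in stage 1, whether or not they enter stage 2, followed through whichever sub-study they enter.* Align the screened-set wording. State in section 14.4.2 that for this set a missing week-12 or week-48 rating counts as non-response.

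Show the rate among stage 2 entrants in an adjacent column, labelled as conditional on stage 2 entry. Both are needed because counting a week-12 responder who declines the optional stage 2 as a week-48 non-responder is conservative.

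The cost is a revised definition, one missing-data sentence and one extra table column, and the descriptive rates will probably look less favourable. No additional data are needed.

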6. GENERAL CONSIDERATIONS

Analysis results will be presented using descriptive statistics. For categorical variables, the number and percentage of subjects in each category will be presented; for continuous variables, the number of subjects [n], mean, standard deviation [SD] or standard error [SE], median, minimum, and maximum will be presented. Statistical comparisons will be tested at two-sided alpha of 0.05 significance level, unless otherwise specified. Data collected in the study will be presented in by-subject listings for all subjects in the full analysis set (efficacy analysis) and safety analysis set

Document: Statistical Analysis Plan

Author: [name]

Version Number: 1.1

Version Date: 18Jan2023

Template No.: CS_TP_BS016 Revision 5

Reference: CS_WI_BS005

Effective Date: 01Apr2018

(safety analysis), unless otherwise specified. All by subject listings will be presented by treatment group, subject identification number in ascending order, unless otherwise specified.

For stage 1 analysis, the analysis period for subjects who enroll stage 2 will be from screening (baseline visit) in stage 1 until before the first dose of stage 2. And for subjects who will not enroll stage 2 (including screen failed subjects before randomization, randomized subjects but not treated, and subjects early discontinued in stage 1), the analysis period will be from screening (baseline visit) in stage 1 until end of study in stage 1. For stage 2 sub-study 1 analysis, the full/safety analysis population will be the randomized subjects who receive at least one dose of study medication or placebo in stage 2, but the analysis period will be from screening (baseline visit) in stage 1 until the end of study in stage 2. But for subjects who will enroll stage 2 sub-study 2, the analysis period will be the date of first dose of the open-label CBP307 0.2mg in stage 2 until the end of study in stage 2 since treatment is changed to open-label CBP307 0.2 mg QD.

For 0.2mg (all stages) group, the analysis period will be the date of first dose of initial administration until the end of stage 2 study, including stage 2 sub-study 1 and stage 2 sub-stage 2.

